Apparatus. The perimetry apparatus (similar to that used for animals, scaled for humans) consists of a ~2m diameter semicircular arena with independently-controlled LEDs (space 2.5°) and speakers (spaced 10°) subtending the central 180° of space embedded in the arena wall. Subjects are seated with their chins in a rest while their eyes are tracked by a high-speed camera (ISCAN ETL200). They acquire fixation of a central spot to initiate a trial (but are not forced to maintain fixation during stimulation). They then make saccades to visual or auditory targets as they appear. Latency of movement and final eye position are recorded. All training, and the training/testing of low-level tasks, takes place in this apparatus. A complementary virtual reality (VR) apparatus provides a platform for training and for testing both low-level and high-level vision, and consists of an HTC Vive Eye Pro with eye-tracking capabilities. Custom software developed in C++ and the Unreal Framework presents visual and auditory stimuli within an immersive 3-D environment. Manual HTC controllers are used to control a set of virtual hands to “point” to targets, with latency and final position of eye, gaze, and hand all tracked and recorded. A microphone records subject verbal responses of confidence in both apparatuses. The VR apparatus provides great flexibility in the delivery of training and testing stimuli, and may be used in either setting.

Multisensory training: Multisensory training is accomplished in the perimetry apparatus under dark (.001 lux) and quiet (~30 dB) ambient conditions. Each session begins with 10 mins of briefing and

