Visual tests: Tests of vision will be conducted on both sides of space and are organized in trials. In each trial the subject acquires fixation for 500 ms before a stimulus is presented after a randomized delay (200-600 ms). Subjects are required to saccade or point to (i.e., “indicate”) the stimulus or stimulus-target (<10° error) within 2 seconds or their response is scored as a “No-Go”. They are informed of whether their response was “correct” or “incorrect” via an auditory tone after a confidence report (see below). Each test has one or more stimulus levels that are manipulated to create the independent variable(s) of psychometric functions of performance. Detection/Localization: Trials contain either a visual target (LED or 5X5° white square) of manipulated contrast at a randomly-selected location outside of central space (correct response: indicate), or no stimulus anywhere (correct response: No-Go). Competition: Trials contain either no stimuli (correct response: No-Go), or 1 stimulus at a randomly-selected location on either side of space (correct response: indicate), or 2 identical visual stimuli at homotopic locations with randomized eccentricity (correct response: indicate both). Stimulus contrast is manipulated. Multisensory Integration: Trials contain either no stimuli (correct response: No-Go) or brief (100 ms) low-contrast visual or low-volume auditory stimuli presented alone or together at a randomly-selected location (correct response: “indicate”). This evaluates whether the senses can be used synergistically in contralesional space to enhance localization as in intact subjects. Frequency Discrimination: Pairs of oriented gratings with manipulated Δ° and Δf presented on either side of space (correct response: indicate if same, No-Go if different). Shape Discrimination: Unilaterally-presented pairs of simple Efron shapes (see (Whitwell et al., 2014)) with manipulated similarity (correct response: indicate if same, No-Go if different). These shapes consist of stacked rectangles or smoothed splines whose similarity can be quantitatively manipulated and provide a robust, common, and controlled way of assessing shape perception in normal and compromised populations. Subjects will also have the opportunity to report qualitative aspects of any changes in their visual perception during the study.

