Analytical Plan. The Humphrey visual field test, kinetic visual field test, and low-vision visual functioning questionnaire (LV-VFQ-48) are standard clinical tests of vision administered before and after training. We expect increases in the number of detected locations and decreases in the thresholds of detection (when detected) at each test location in the hemianopic field, for at least Goldmann size V stimuli and smaller, and significant improvements in quality of life. In addition to these common clinical assays, a more detailed picture of low- and high-level vision will be obtained from the tests described above, which produce psychometric functions (curves relating % correct responses to stimulus level) for each subject and location or side of space. Parameters of these functions describing thresholds and maximum accuracy will, alongside confidence scores and latency, be evaluated for changes over time and across subjects and sides of space in a multilevel multivariate regression model (Gelman and Hill, 2007). Maximum likelihood estimation will be used to estimate parameter distributions to guide future studies.

Human Subjects Protection

Subject Recruitment Methods. Patients will be recruited from the local subject population hospitalized/seen by Neurology at Atrium Health / Wake Forest School of Medicine. To maximize the potential for success, adults (<85) of either sex will be selected based on: (1) diagnosis of a stable homonymous hemianopia (>4 weeks) with absence of hemineglect, (2) a lesion encompassing at least primary visual cortex but sparing parietal cortex, (3) normal auditory and cognitive function, (4) willingness to participate in the three month program, (5) ability to perform the visual discriminations in their intact field. Subjects not meeting these criteria are either poor candidates for rehabilitation given the extent of the deficit relative to the known circuits responsible for recovery in animals (crit. 1-2), will not be suitable for the visual-auditory training paradigm (crit. 3-4), or have visual capabilities that cannot be adequately tested (crit. 5). Multiple (n=6) subjects will be recruited for left- and right-sided lesions. Because this is a pilot program, variance across other demographics (e.g., age, gender, race, stroke type) will be noted but are unlikely to be able to be statistically evaluated.

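### The Multisensory Integration test is meant to show better localization, but the plan scores only a hit within 10°, names no angular-error outcome, and sets no same-side rule for targets near the midline

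*Combined protocol and SAP*

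**What the plan says.** All references are to the combined protocol and SAP.

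- **Aim.** Under Visual tests, the Multisensory Integration test has a localization purpose: "This evaluates whether the senses can be used synergistically in contralesional space to enhance localization as in intact subjects". Its stimuli are "brief (100 ms) low-contrast visual or low-volume auditory stimuli presented alone or together at a randomly-selected location".
- **Scoring.** The same section requires a saccade or point that lands on the target, "<10° error) within 2 seconds or their response is scored as a" No-Go.
- **Recording.** Under Apparatus, for the perimetry arena: "Latency of movement and final eye position are recorded". The virtual-reality set-up stores final eye, gaze and hand position. Under Design, final position is also extracted from the movement video and is to be analysed, in general terms, for change during the study and for prognostic value.
- **Analysis.** The Analytical Plan builds psychometric functions, "curves relating % correct responses to stimulus level) for each subject and location or side of space". It then models their thresholds and maximum accuracy together with confidence and latency. Neither angular error nor end position is named.
- **Target positions.** Detection/Localization targets appear "at a randomly-selected location outside of central space (correct response: indicate"; the extent of central space is not given. A Competition trial may contain no stimulus, two stimuli, "or 1 stimulus at a randomly-selected location on either side of space". Neither Competition nor Multisensory Integration states a central exclusion, and no test requires the end point to be on the target's side.

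**The concern.** The question is how accurately a person localizes, but the score records only whether the end point fell inside a 10° window. Two things are lost. Within the window, an end point 1° off and one 9° off are the same. Outside it, a prompt response 12° off receives the same code as no response, so failure to detect and failure to localize are merged. A real gain in precision from adding sound, or over training, may then show weakly or not at all in the modelled quantities, although the data to show it are on file.

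The midline point concerns what a blind-field hit means. A window centred less than 10° from the vertical meridian extends into the seeing field. Design and Outcome Measure(s) frame the main hypotheses as all-or-none and treat any regained visual function as a success. Under that criterion, even a few hits that landed on the seeing side could be read as recovery.

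**Working it through.** **1. The plan's own figures.** The plan gives no power, significance level or localization-error SD for these tests, so there is no design figure to reproduce. The one related figure, 20 to 96 trials per block (Testing structure), checks as runs × trials × levels: 2 × 10 × 1 = 20 and 2 × 12 × 4 = 96. One block therefore gives 2 × 10 = 20 to 2 × 12 = 24 trials per stimulus level. I use 24 trials per condition, and 48 for two blocks.

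**2. Assumptions (not in the documents).** One-dimensional, unbiased Gaussian end-point error; independent trials; two-sided 5% level; the SDs in the table.

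**3. Hit rate.** P(hit) = 2Φ(10/SD) − 1. For SD 6°, 2Φ(1.667) − 1 = 90.4%; for SD 4°, 2Φ(2.5) − 1 = 98.8%.

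**4. Power.** By simulation: Fisher's exact test on hits against the Mann-Whitney test on absolute error.

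| SD change | Trials per condition | Hit rate | Power, hit | Power, absolute error |
|---|---|---|---|---|
| 5° to 3.5° | 24 | 95.4% to 99.6% | 0.3% | 26% |
| 5° to 3.5° | 48 | 95.4% to 99.6% | 2% | 48% |
| 6° to 4° | 24 | 90.4% to 98.8% | 6% | 32% |
| 8° to 5° | 48 | 78.9% to 95.4% | 58% | 68% |
| 10° to 6° | 48 | 68.3% to 90.4% | 71% | 76% |
| 12° to 8.4° | 48 | 59.5% to 76.6% | 35% | 46% |

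Repeat runs differ by a few points (68% to 71% for absolute error in the 8° to 5° row). Absolute error does better in every row. The gap is large near ceiling and modest away from it.

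**5. Midline geometry in the arena.** LEDs are 2.5° apart over 180°. Counting from 2.5° to 90° gives 90/2.5 = 36 positions per side. The window reaches 10° minus the target's eccentricity past the midline: 7.5° for a target at 2.5°, 5° at 5°, and 2.5° at 7.5°. As a share of the 20° window, that is 37.5%, 25% and 12.5%. So 3 of 36 positions (8%) per side are affected if none is excluded.

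**6. Which tests are exposed.**
- *Detection/Localization:* only if central space is narrower than 10°.
- *Competition, single target:* exposed as written.
- *Multisensory Integration:* light-alone trials could use any LED, but sound and paired trials in the arena follow the speakers, which are 10° apart. If an even grid includes the 45° training position, the innermost speaker is at 45 − 4 × 10 = 5° (1 of 9 per side) and its window reaches 5° across. If the grid is centred on 0°, the innermost is at 10° and no window crosses.

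**The case against.** **End position is not thrown away.** A reader might infer that it is. The documents do not support this: it is stored, Design plans an analysis of final position from the video, and the list of measures in Outcome Measure(s) is left open. What stands is narrower: none of these makes error relative to the target a localization outcome or puts it in the model.

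**Ceiling is conditional.** A reader might also infer that the hit score can never show better localization. The test uses weak, brief stimuli, and Testing structure tailors levels to each subject's limits, both of which push performance below ceiling. There the hit score responds (71% against 76% for 10° to 6°), and benefit may also appear in thresholds, latency or confidence. The near-blindness applies only where errors are already well under 10°.

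**Near-midline false hits are not close to certain.** That reading would require an eye resting at fixation to count as indicating a nearby target. The scoring rule asks for a saccade or point and otherwise records No-Go, so a false hit needs an actual response into the window. For illustration, assume 30 blind-side trials, uniform draws over 36 LEDs, and a stray response into the window on 2%, 5% or 10% of unseen near-midline trials. The chance of at least one false hit, 1 − (1 − r × 3/36)^30, is then 5%, 12% or 22%. A constant artefact would also appear at baseline, where the same battery is run.

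**The hit has its own purpose.** The hypotheses are qualitative, and the hit answers whether the task can be done at all. Angular error exists only on trials with a response, so newly detected weak targets may worsen its mean as vision recovers. Both points stand: error should be added, not substituted.

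**No single two-condition test is planned.** True; the model is for estimation. The power figures only compare the information in the two scores, and that comparison carries over to precision.

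**Conclusion.** The concern holds in a limited form. The plan says one test evaluates enhanced localization, but it names no outcome that measures localization beyond a 10° hit, although the needed data are recorded. The cost runs from severe near ceiling (6% against 32% power for SD 6° to 4° with 24 trials) to small away from it (71% against 76% for 10° to 6° with 48 trials). These figures rest on assumed SDs, Gaussian unbiased error and independent trials; the documents give nothing to choose among the rows.

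The midline gap is real but small: 3 of 36 LED positions per side if none is excluded. It chiefly affects single-target Competition trials. For Multisensory Integration it depends on an unstated speaker layout, and for Detection/Localization on an undefined exclusion zone. It should be closed because the success criterion is all-or-none, not because false hits are shown to be frequent.

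**What to change.** 1. In the Analytical Plan, add signed and absolute angular error, computed from the recorded end positions, to the multilevel model as a localization outcome for Multisensory Integration and Detection/Localization.
2. Report it beside the response rate, since error is observed only when the subject responds, and alongside the 10° hit, not in place of it.
3. In all location tests, count a hit only if the end point is on the target's side, or report targets under 10° separately. State the extent of central space in degrees, and say whether it applies to Competition and Multisensory Integration.

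The cost is plan wording, a scoring or target-list setting, slightly more analysis, and a few near-midline trials handled separately. No extra measurement or visit is needed.

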Outcome Measure(s). A variety of dependent measures are extracted during these experiments, including responses selected, response delay/timing, response accuracy, etc. Responses to visual stimuli will be evaluated over the duration of the experiment to assess recovery of function. The main hypotheses state that subjects will either be able to perform some task at some level or not at all, although there is likely to be quantitative variation in parameters such as response latency, threshold sensitivity, and confidence. In this context, recovery of any visual function is a success. Below we outline two sets of predictions identifying the most credible outcomes and elaborate on the significance of each, although mixed results are also possible.

Modest Rehabilitation: It is possible that hemianopic patients will recover basic reflexive visual functionality, but their capabilities will be limited to those typically associated with “blindsight”. In this case, they would be able to detect and localize visual stimuli in the rehabilitated field and use auditory information to enhance this capability. However, they would always choose the intact field in competition tasks, be unable to perform any higher-order discriminations in the contralesional field, and would always

have low confidence in that field even when they can perform visually – a result falling short of that seen in the animal model. Such a result will be less than expected but is not without clinical value: by acquiring the ability to respond to contralesional visual stimuli, rehabilitated subjects can bring them into the sighted field for further analysis.

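### In the discrimination tests, withholding a response is scored as correct on *different* pairs, so raw percent correct depends on trial mix and response habit as well as on vision

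*Combined protocol and SAP*

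**What the plan says.** All references are to the combined protocol and SAP.

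- **Visual tests, response rule.** Subjects must saccade or point to "the stimulus or stimulus-target (<10° error) within 2 seconds or their response is scored as a “No-Go". Read plainly, a missing response and an off-target response are both recorded as No-Go.
- **Visual tests, discrimination.** Both Frequency and Shape Discrimination use the key "correct response: indicate if same, No-Go if different". The shape test uses "Unilaterally-presented pairs of simple Efron shapes", so the whole pair can lie in the blind field. The gratings appear on either side of space, and the text does not say whether both share a side.
- **Visual tests, Competition.** Double trials present "2 identical visual stimuli at homotopic locations with randomized eccentricity (correct response: indicate both".
- **Testing structure.** A run is 10-12 trials at one stimulus level. A block mixes two runs at 1-4 levels, 20-96 trials in all. Levels are customised by subject and narrow over sessions.
- **Analytical Plan.** The tests yield "curves relating % correct responses to stimulus level". Thresholds and maximum accuracy are modelled over time, across subjects and across sides of space.
- **Outcome Measure(s).** "In this context, recovery of any visual function is a success".

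The plan gives no *same*:*different* ratio, chance level, pass mark, or correction for false alarms or response bias.

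**The concern.** The correct answer to a *different* pair is the same recorded event as seeing nothing. In the shape test the manipulated quantity is similarity, so every level with a non-zero difference is a *different* level, and a hemifield without vision can sit at maximum accuracy on all of them. Part of the analysed curve then measures willingness to respond.

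The consequences matter for how the pilot is read. The protocol's modest result is defined partly by inability to make any higher-order discrimination in the contralesional field. The expected result is defined by ability to perform each task at some level under some conditions. Both are stated as absolute abilities, without a pass mark, and the discrimination and Competition tests are what tell them apart. The results are meant to support funding and larger trials.

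**Working it through.** **Reproducing the plan's figure.** Block size = 2 runs × number of levels × trials per run. This gives 2 × 1 × 10 = 20 and 2 × 4 × 12 = 96, matching the stated 20-96. Each level therefore has 20-24 trials per block.

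**Never-respond observer, blind field.** Every trial is a No-Go, so *different* pairs score 100% and *same* pairs 0%. A run at one *different* level scores 10/10 or 12/12. If chance were 50% (an assumption; the plan gives no chance level), those scores would have probability 0.5^10 = 0.00098 and 0.5^12 = 0.00024.

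**Overall percent correct** equals f, the share of *different* pairs. Assume *same* is one level and the other one to three levels are *different*:

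| *same*:*different* | correct / trials | % correct |
|---|---|---|
| 1:1 | 20/40 or 24/48 | 50% |
| 1:2 | 40/60 or 48/72 | 67% |
| 1:3 | 60/80 or 72/96 | 75% |

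Moving from 1:1 to 1:3 between sessions adds 75 − 50 = 25 points with no vision. With the mix and strategy held constant, the change from baseline is 0.

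**Shift in response criterion.** Let a non-seeing subject guess on every trial and land within 10° with probability q (assumed 5-20%). *Different* pairs score 1 − q = 80-95% and *same* pairs score q = 5-20%. If q = 20% and the subject later stops responding, *different* accuracy rises from 80% to 100% and *same* accuracy falls from 20% to 0%. Overall accuracy is (1 − f)q + f(1 − q):

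- at 1:1 it stays at 50%;
- at 1:3 it goes from 0.25 × 0.20 + 0.75 × 0.80 = 65% to 75%.

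Feedback on correctness therefore favours withholding only when *different* pairs are the majority.

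**Game score.** Under Confidence reports, a correct trial earns twice the wager and an incorrect trial loses the wager. Always withholding earns 2wf − w(1 − f) = w(3f − 1) per trial. At 1:1 this is +0.5, +1.0 and +1.5 for wagers 1, 2 and 3; at 1:3 with wager 3 it is +3.75. It is positive whenever f exceeds 1/3, so above that share reporting top confidence pays even when nothing is seen. Confidence is itself an analysed outcome.

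**Competition.** The two stimuli on a double trial are at homotopic positions, so the intact-side stimulus reveals where the other one would be. Always indicating both whenever an intact-side stimulus is seen is correct on 100% of doubles and wrong on every intact-side single. Assuming equal thirds of none, one and two stimuli, with singles split equally by side, it is correct on (1/3)/(1/3 + 1/6) = 2/3 of trials with an intact-side stimulus.

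**Corrected metric.** Balanced accuracy for the never-respond observer is (0% + 100%)/2 = 50% at any mix. For the guesser it is (q + 1 − q)/2 = 50%. D-prime is 0 with equal numbers of *same* and *different* trials. With unequal numbers, the usual log-linear correction for zero counts gives a spurious 0.41 (24 and 72 trials) or 0.42 (20 and 60), a further reason to keep the numbers equal.

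**The case against.** The strongest reply is that the plan already contains the means of exposing a non-responder.

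- *Same* pairs need an on-target response, so such a subject scores 0% there. If *same* is plotted as the zero-difference level, the curve would look plainly abnormal.
- Detection/Localization targets also need an on-target response, and blank trials are included.
- The battery is run at baseline, the stated outcome is recovery, and the model looks at change over time.
- Higher-order tests are not pursued extensively until lower-level ones are intact.
- Perimetry and the quality-of-life questionnaire do not use this scoring.
- In Competition, a subject who always indicates both would be caught on intact-side singles.

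Most of this stands, and it rules out two stronger readings. A reader might infer that the outcome cannot distinguish absent vision from discrimination; the *same* pairs can do so if they are scored separately. A reader might also infer that the success rule can hardly fail. Withholding fails every target-present detection trial, and the documents give no significance level, pass mark or chance level from which a family-wise error rate could be computed.

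The remainder is not answered. The plan does not say that *same* and *different* pairs will be reported separately, or that their ratio is fixed. Test content is customised over sessions, so a comparison with baseline need not be like for like. Limiting higher-order tests until detection returns does not protect the modest-versus-expected distinction, which concerns subjects whose detection has already recovered. Separate scoring afterwards could recover hit and false-alarm rates, but not whether a given No-Go meant a judgement of *different* or no percept at all.

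**Conclusion.** The point holds in limited form. For Shape Discrimination, a blind hemifield that never responds reaches 100% at every non-zero difference level and 0% on *same* pairs. Overall percent correct then reflects only the unstated mix. The same applies to Frequency Discrimination if both gratings fall in the blind field, which the text leaves open. Where baseline is already at 100%, real gain at those levels cannot show.

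Apparent recovery requires something to change. An assumed shift in mix from 1:1 to 1:3 adds 25 points. An assumed move from guessing (q = 20%) to withholding adds 20 points on *different* pairs, and 10 points overall at 1:3. With neither change, the difference from baseline is zero. The mixes and q are assumptions; the scoring rule and the percent-correct analysis are the plan's own.

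In Competition, correct doubles alone do not demonstrate blind-field vision. The scoring blurs the modest-versus-expected classification, but it does not invalidate the detection tests, the clinical field tests or the pilot as a whole.

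**What to change.** 1. Require an explicit *different* response, by verbal report or pointing device (both already permitted under Interventions and Interactions), and code no response as its own category.
2. State the *same*:*different* ratio, preferably 1:1, and hold it fixed across sessions. Stimulus levels can still be customised.
3. Replace raw percent correct with hit and false-alarm rates, summarised as d-prime or balanced accuracy at each level.
4. In Competition, compare blind-side indication on double trials with blind-side indication on intact-side singles.
5. Count a function as recovered only if sensitivity exceeds the matched null-trial rate and the subject's own baseline.
6. State whether both gratings in a Frequency Discrimination pair fall on the same side.

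The cost is small: somewhat longer response instructions, a change to response coding in the custom software, and revised Analytical Plan wording. The response coding should be settled before testing begins, because trials already recorded as No-Go cannot later be divided into *judged different* and *saw nothing*.

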Testing conditions: Each of the above tests will be evaluated under two different ambient light conditions: normal indoor levels (~300 lux) and darkness (~.001 lux). Lighting conditions are set during the “briefing” period and changed during the “break” (see below), which gives time for dark- or light-accommodation. We will also evaluate conditions in which stimuli are either stationary or moving.

Confidence reports: Subject performance is tracked online and summarized in a numeric “game score” displayed to them after each testing run (see below). On each trial, after making their response (either indicating or No-Go), subjects verbally report a confidence score of 1-3 indicating their confidence in whether they are guessing (1), are unsure (2), or are very confident (3) in their response. The confidence rating translates to the points wagered for that trial. Correct responses increase the game score by double the wagered amount, while incorrect responses decrease the score by the wagered amount.

Testing structure: A 2 hr testing session is divided into two 45-min sets separated by a 10 min “break”, with a 10 min “briefing” period at the beginning and 10 min “recapitulation” period at the end.

Training/testing sessions contain only a single set. Each trial requires <3-5 seconds. Trials of a single task, stimulus level, and testing condition are conceptually organized into “runs” of 10-12 trials (~.75-1 min/run with warmup/cooldown). Two runs with the same task and testing condition, but 1-4 stimulus levels, are intermixed within a “block” of 20-96 trials (2-8 min/block). This structure provides ample time to test two blocks of each visual test (e.g., one block stationary, the other moving) within each set. However, testing will be customized for each subject in this pilot to focus on performance limits; e.g., by reducing testing of basic capabilities in later sessions, not extensively testing multiple levels of higher-order capabilities when lower-level ones are not yet intact, and initially testing with wider ranges of stimulus levels before proceeding to narrower ranges.

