The Expected Result: However, our expectation is that hemianopic patients will recover visual functionality similar to that observed in the animal model, although the timing of the recovery and the quantitative parameters of the functional endpoints may differ. This means that, after a few weeks of training, they will be able to perform each of the tasks at some level under some conditions. We expect performance to be best under scotopic conditions and for moving stimuli; i.e., testing conditions best suited to driving robust visual responses in SC-mediated visual pathways. There is likely to be an initial separation between performance in visual tasks and confidence, with the former recovering faster than the latter, as the brain adapts and reinterprets activity patterns in remaining circuits as definitive of the visual stimuli generating them.

In either case, future directions will examine the means to improve the rehabilitation method (including calibrating subjects to the sensation of contralesional visual stimuli), examining the impact of the strategy on other domains impacting quality of life (e.g., navigation), an analysis of the underlying circuits using magnetoencephalography, evaluation of the sensitivity of different individual features to the procedure (e.g., age, gender, delay from lesion onset to treatment), a deeper exploration of the limits of functional recovery, and the formalization of a clinical trials protocol.

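### The confidence wager pays most for the top rating at any accuracy above one third, so confidence ratings are open to upward drift that the single-arm design cannot cleanly separate from recovery

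*Combined protocol and SAP*

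**What the plan says.** Under Methods and Measures, Confidence reports, participants state after every test response "whether they are guessing (1), are unsure (2), or are very confident (3) in their response". The rating is also a bet: "The confidence rating translates to the points wagered for that trial". The pay-off is then given: "Correct responses increase the game score by double the wagered amount, while incorrect responses decrease the score by the wagered amount". The running total is "displayed to them after each testing run". The Visual tests paragraph adds that each response is declared right or wrong "via an auditory tone after a confidence report (see below").

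Confidence is used in three places:
- The Analytical Plan enters confidence scores, with psychometric parameters and latency, in a multilevel regression over time, subjects and sides of space.
- Outcome Measure(s) lists, among the marks of modest rehabilitation, that patients would always "have low confidence in that field even when they can perform visually".
- The Expected Result forecasts that performance will return before confidence: "There is likely to be an initial separation between performance in visual tasks and confidence".

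**The concern.** A wager tells us about confidence only if the participant does best by reporting what he or she believes. Here gain and loss both rise in proportion to the rating, so the score favours one of the two extreme ratings and never the middle one. The switch between them comes at an accuracy that many responses could exceed.

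The tone on every trial lets participants learn how often they are right, and the displayed total lets them learn which wagers pay. Sessions run weekly for three months. All six participants are trained, and the Design paragraph describes no comparison group. A participant who gradually learns that betting high pays would show confidence rising over sessions, which is also how returning visual awareness would look. The regression estimates are meant to guide future studies, so a drift of this kind would be carried forward.

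**Working it through.** The plan states no break-even accuracy or other figure on this point, so there is nothing to reproduce first.

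**Inputs**
- Wager w = 1, 2 or 3; pay-off +2w if correct, −w if incorrect (Confidence reports).
- Runs of 10 to 12 trials (Testing structure).
- Same/different tests: two possible responses, for example shape pairs "with manipulated similarity (correct response: indicate if same, No-Go if different"). *Assumption:* equal numbers of same and different trials, so guessing gives p = 0.5. The mix is not stated.
- Guessing a location: a response must fall within 10° (Visual tests) and the array covers 180° (Apparatus). *Assumption:* a 20° window guessed at random gives 20/180 = 0.11, or 20/90 = 0.22 if the side is known.
- Always withholding a response: accuracy equals the share of no-stimulus trials, which is not stated for the tests.

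**Step 1: expected score per trial**

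E = 2w·p − w·(1 − p) = w(3p − 1)

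The sign of 3p − 1 decides everything. If p > 1/3, E rises with w and rating 3 is best. If p < 1/3, E falls with w and rating 1 is best. At p = 1/3 all three tie at zero.

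| p | Rating 1 | Rating 2 | Rating 3 | Best |
|---|---|---|---|---|
| 0.11 | −0.67 | −1.33 | −2.00 | 1 |
| 0.22 | −0.33 | −0.67 | −1.00 | 1 |
| 1/3 | 0 | 0 | 0 | tie |
| 0.34 | 0.02 | 0.04 | 0.06 | 3 |
| 0.50 | 0.5 | 1.0 | 1.5 | 3 |
| 0.70 | 1.1 | 2.2 | 3.3 | 3 |
| 0.90 | 1.7 | 3.4 | 5.1 | 3 |

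**Step 2: would a participant notice?**

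With a constant rating w and k correct out of n, a run scores w(3k − n). At p = 0.5 the expected run score for ratings 1/2/3 is 5/10/15 for n = 10 and 6/12/18 for n = 12. All 3s beat all 1s whenever k > n/3. That needs at least 4 of 10 (probability 0.83) or at least 5 of 12 (probability 0.81). The advantage would show in most displayed scores.

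**Step 3: where does guessing exceed 1/3?**
- Same/different tests: yes, if trial types are roughly balanced (0.5).
- Guessing a location: no (0.11 to 0.22). There rating 1 pays best, in agreement with its label.
- Always withholding a response: only if no-stimulus trials exceed one third of the trials the participant cannot tell apart.

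**Step 4: set against the plan's predictions**

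Both predictions that involve confidence require low ratings at good accuracy. At an illustrative p = 0.7, a participant who performs well but feels unsighted earns 1.1 per trial by reporting 1 and 3.3 by reporting 3. The score therefore works against the dissociation the study hopes to observe.

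**The case against.** The strongest reply is that the algebra describes someone who plays for points. Participants are asked to use the ratings by their verbal labels, and no money or other reward beyond the displayed score is described. Nothing in the documents shows that participants will chase the score. A reader might infer that confidence is no longer a valid outcome. The documents do not support that; they support only that the rule leaves it open to bias.

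A reader might also infer that the top rating pays best for a guesser in every task. Step 3 shows otherwise, and detection and localization are the functions the plan thinks most likely to recover.

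Nor does the predicted lag of confidence behind performance become uninterpretable. Once accuracy exceeds 1/3 the incentive is upward, so low ratings given in spite of it are, if anything, conservative evidence of a dissociation. It is the later rise that is ambiguous.

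The plan has partial safeguards. Tests are run on both sides of space and side is in the model, so a general change in betting style might also appear in the intact field. Unwagered qualitative reports and a diary are collected too. These help only in part. Eligibility requires that participants can do the discriminations in the intact field, so ratings there may already be high, with little room to show a shift. The diary has no set format.

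Finally, the main hypotheses ask whether a task can be performed at all. The other marks of modest rehabilitation, in competition and in higher-order discrimination, do not use the wager. That limits the weight of the point but does not remove it.

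**Conclusion.** The point holds in limited form. The pay-off result is exact: for a participant who maximises expected score, rating 3 is best at every accuracy above 1/3, and rating 2 is never strictly best. At p = 0.5 a high bet triples the expected score (1.5 against 0.5).

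Extending this to pure guessing rests on an assumed balance of same and different trials, and it fails for guessed locations under the assumed chance of 0.11 to 0.22. The bias itself depends on participants responding to the score, which is possible but not shown. The consequence is therefore specific: a rise in confidence over sessions may be partly learning of the pay-off, and the design cannot cleanly separate the two. Accuracy, thresholds and latency are not directly scored by the wager. This is a cheap improvement to a secondary measure in a six-person pilot.

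**What to change.** Base the displayed game score on accuracy only, and collect the 1–3 confidence report without points. This takes a small change in the task software and a revised protocol sentence. The cost is a slightly less engaging game and confidence reports with no incentive behind them.

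If a wager is kept, use a non-linear pay-off in which each rating is best in its own accuracy band, with the bands set in advance against each task's chance level. A symmetric +w/−w rule is not enough: it moves the switch point from 1/3 to 1/2 and still never favours rating 2. One schedule should not be applied to all tasks either. Take correct/incorrect pay-offs of +1/0, +2/−2 and +3/−6:
- The expected scores are p, 4p − 2 and 9p − 6, which cross at p = 2/3 and p = 0.80.
- Rating 1 is then rewarded up to p = 0.67. A participant localizing at p = 0.60, far above the assumed chance, would earn 0.6, 0.4 and −0.6 for ratings 1, 2 and 3, and so be paid to claim to be guessing.
- That would push towards the low-confidence pattern that marks modest rehabilitation.

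In either case, state the shares of no-stimulus, same and different trials in each test, so that chance accuracy is known.
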